## **14 ETHICS/PROTECTION OF HUMAN SUBJECTS**

### **14.1 Ethical Standard**

The investigators will ensure that this study is conducted in full conformity with the principles set forth in The Belmont Report: Ethical Principles and Guidelines for the Protection of Human Subjects of Research, as drafted by the US National Commission for the Protection of Human Subjects of Biomedical and Behavioral Research (April 18, 1979) and codified in 45 CFR Part 46 and/or the ICH E6.

### **14.2 Institutional Review Board**

The protocol, informed consent form(s), and all participant materials will be submitted to the IRB for review and approval. Approval of both the protocol and the consent form must be obtained before any participant is enrolled. Any amendment to the protocol will require review and approval by the IRB before the changes are implemented in the study. A progress report will

be submitted by the Study CRO Program Lead to the IRB at intervals specified by the IRB, but not less than annually.

### **14.3 Informed Consent Process**

Informed consent is a process that is initiated prior to the individual agreeing to participate in the study and continues throughout study participation.

The participating Site Investigator will ensure that written informed consent (and/or assent, if applicable) is obtained from each subject (and parent(s) or legal guardian(s), if applicable) in accordance with applicable regulations. Subjects under the age of 18 must sign the Assent Form. The subject and their parent(s) or legal guardian(s), if applicable, will be given adequate time to consider the risks associated with participation in the study. Study Subjects may provide consent/asset using online data collection portal, in case of virtual study visits/encounters in the absence of in-person visits/encounters. Each subject will provide informed consent (and/or assent if applicable and according to IRB regulations) prior to participating in any study procedures, as outlined in Section 6.3.2 of this protocol. As an addendum to the main consent form, the Subjects from a small subset of sites will be consented (with necessary assent) to allow facial photographs taken at baseline and Week 12 by their clinician at the privacy of the clinician's office and will be consented (with necessary assent) to provide a 1-3 minute testimonial of Subject's experience with sarecycline (Seysara®) at Week 12.

### **14.4 Participant Confidentiality**

Participant confidentiality is strictly held in trust by the investigators, study staff, and the sponsor(s) and their agents. The final research data will constitute only **de-identified** data, for research analyses and reporting. Participants will be identified by a unique study ID number assigned by the site coordinator and/or study CRO, which will be listed on the paper-based consent forms or online e-consent forms and on each of the online e-DCFs. The site coordinator and the CRO project team may review the e-DCFs for any missing data periodically. Access to

---

the online e-DCFs will be restricted to the patient/caregiver, the site coordinator/Investigator, and the relevant representatives from the CRO.

The study protocol, documentation, data, and all other information generated will be held in strict confidence. Site Investigator and study subject contact information will be collected strictly for administrative purposes, such as processing of incentives and to share study follow-up reminders. This personally identifiable information will remain separate from research data.

Photographs to document baseline clinical status and Week 12 outcomes (of acne severity) associated with the use of study medication will be obtained from a small subset of study Subjects. Audio testimonials depicting Subject's experience with sarecycline may be obtained from a subset of study Subjects at Week 12. All of these data will be stored electronically and anonymized (using appropriate digital technology) before using this data for further analyses and/or publications.

No information concerning the study or the data will be released to any unauthorized third party without prior written approval of the sponsor or the study CRO. The study CRO or other authorized representatives of the sponsor may inspect all study documents and records, but at no juncture will study subject identifiable information will be collected or disclosed.

## **15 OTHER INFORMATION**

### **15.1 Publication and Disclosure Policy**

Publication and disclosure policy is addressed in a separate agreement.

### **15.2 Termination of the Study**

If the study is terminated prematurely or suspended, the appropriate IRB will be promptly informed of the termination or suspension and will be provided the reason(s) for the termination or suspension. All obligations and responsibilities of the Sponsor and the Investigator will remain in force if the study is terminated prematurely.

## 17 APPENDICES

*Appendix A: Study Schedule of Events*

*Appendix B: Select Study Questionnaires*

*Appendix C: Signature Page*

## 17.1 APPENDIX A: Study Schedule of Events

Study Encounter (physical or virtual)	Baseline E1	E2	E3	End of Study E4	Early Termination Visit
Week †		Wk 4 (± 4 d)	Wk 8 (± 4 d)	Wk 12 (± 4 d)	-
Informed consent	X				
Selection criteria	X				
Demographics & baseline clinical characteristics 	X				
Physical examination 	X			X	X
AV medical history and relevant comorbidites 	X			X	X
Seysara dose 	X	X	X	X	X
Dispensing and return of study medication	X	X	X	X	X
Prior acne medication (since diagnosis & past 6 months)	X				
Concomitant general medication	X			X	X
Concomitant anti acne medication	X			X	X
Site Investigator's clinical assessment of acne 	X	X	X	X	X
Study subject questionnaires 	X	X	X	X	X
AEs/SAEs 	X	X	X	X	X
Reasons for premature study withdrawal					X

† Expected in-person or virtual encounter/visit schedule, in relation to the index date (date of first administration of sarecycline).

 Clinical characteristics data assessed retrospectively based on what is documented in patient medical charts.

 Routine physical examination conducted as part of usual care alone and as documented in patient medical charts; such data may include - blood pressure, waist circumference, height/weight measurements.

 May include AV date of diagnosis, baseline severity, relevant comorbidities, per clinician judgment and/or as documented in patient medical charts immediately before the index date; new emerging comorbidities during the study period will be recorded, based on the documentation in patient medical charts.

 Expected usage is once daily, every day during the duration of the trial.

 Site Investigator assessments of AV severity of Subjects may be conducted during subject visit to clinician offices, or via remote/virtual (telehealth) visits owing to Covid-related travel restrictions.

 Subject self-assessments will include PtGA of acne severity; various HRQOL assessments will be conducted at baseline and Week 12.

 In the case of premature study discontinuation due to an AE, the Investigator should make every effort to collect the AE duration and outcome. Any SAE that is ongoing at the End of the Study or at the time of premature withdrawal will be followed up until the SAE is resolved or at least up to 4 weeks. AE follow-up information will be reported in the eDCF.

Note: AE, adverse event; eDCF, electronic Data Collection Form; E, encounter; W, week.

## 17.2 Appendix B: Select Study Questionnaires

### ASIS

Please read and answer each of the following questions about **acne signs and symptoms**. Before answering each question, **look in the mirror and think about the acne on your face**. Select one answer for each question that best describes your experience with acne **right now**. There are no right or wrong answers.

1. How oily is your face right now?

Not at all	A little	Somewhat	Quite a bit	Very
				

2. How many pimples do you have on your face right now?

None	A few	Some	Quite a bit	A lot
				

3. How many acne scars (holes or indents) do you have on your face right now?

None	A few	Some	Quite a bit	A lot
				

4. How many scabs from acne do you have on your face right now?

None	A few	Some	Quite a bit	A lot
				

5. How many dark marks from acne do you have on your face right now?

None	A few	Some	Quite a bit	A lot
				

6. How many blackheads do you have on your face right now?

None	A few	Some	Quite a bit	A lot
				

7. How many whiteheads do you have on your face right now?

None	A few	Some	Quite a bit	A lot
				

8. How much redness do you have on your face right now?

None	A few	Some	Quite a bit	A lot
				

9. Overall, how is the acne on your face right now?

Clear	Almost clear	Mild	Moderate	Severe
				

Please read and answer each of the following questions about how **acne impact your quality of life**. Before answering each question, look in the mirror and think about the acne on your face. Select one answer for each question that best describes your experience with acne in the past 7 days. There are no right or wrong answers.

10. Over the past 7 days, rate how your face looked because of your acne.

Excellent	Very good	Good	Fair	Bad
				

11. Over the past 7 days, how often did you feel sad because of the acne on your face?

Never	Rarely	Some of the time	Most of the time	All of the time
				

12. Over the past 7 days, how often did you feel embarrassed because of the acne on your face?

Never	Rarely	Some of the time	Most of the time	All of the time
				

13. Over the past 7 days, how often did you feel self-conscious because of the acne on your face?

Never	Rarely	Some of the time	Most of the time	All of the time
				

14. Over the past 7 days, how often did you feel annoyed because of the acne on your face?

Never	Rarely	Some of the time	Most of the time	All of the time
				

15. Over the past 7 days, how often did you feel not confident because of the acne on your face?

Never	Rarely	Some of the time	Most of the time	All of the time
				

16. Over the past 7 days, how often did you choose not to be around other people because of the acne on your face?

Never	Rarely	Some of the time	Most of the time	All of the time
				

17. Over the past 7 days, how often did someone make bad comments about the acne on your face?

Never	Rarely	Some of the time	Most of the time	All of the time
				

### Expert Panel Questionnaire

Please read and answer each of the following questions about how **acne affect your emotional wellbeing, social interactions, and other daily activities**. Before answering each question, look in the mirror and think about the acne on your face. Select one answer for each question that best describes your experience with acne over the past 7 days. There are no right or wrong answers.

1. Over the past 7 days, how often has your acne made you feel angry (mad/sad)?

Never	Rarely	Some of the time	Most of the time	All of the time
				

2. How worried are you about how long your acne will last and how bad it will get?

Not at all	Slightly	Somewhat	Moderately	Extremely
				

3. How often do you think about your acne?

Never	Rarely	Some of the time	Most of the time	All of the time
				

4. Over the past 7 days, how worried have you been about your acne?

Not at all	Slightly	Somewhat	Moderately	Extremely
				

5. How often do you change, edit, or filter your social media photo or selfie because of your acne?

Never	Rarely	Some of the time	Most of the time	All of the time
				

6. How often does acne impact your “in real-life” plans (IRL) (like dating or social engagements, playing sports, swimming or hanging out)?

Never	Rarely	Some of the time	Most of the time	All of the time
				

7. How often are you doing something to hide your acne (like mess with, squeeze/pop, or use makeup, concealer, hairstyle, clothes to cover up)?

Never	Rarely	Some of the time	Most of the time	All of the time
				

8. How often do you feel picked on or judged because of your acne?

Never	Rarely	Some of the time	Most of the time	All of the time
				

9. How concerned are you that your acne will affect your ability to reach your future goals (in school or work) and be the best you can be?

Not at all      Slightly      Somewhat      Moderately      Extremely  
                       

10. Over the past 7 days, how often has worrying about or discomfort (itching/hurting) from acne affected your sleep?

Never      Rarely      Some of the time      Most of the time      All of the time

## LIST OF ABBREVIATIONS

ADR	Adverse Drug Reaction
AE	Adverse Event/Adverse Experience
App	Application / Mobile Application
Approx.	Approximately
ASIS	Acne Symptom and Impact Scale
AV	Acne Vulgaris
CASRO	Council of American Survey Research Organizations
CFB	Change From Baseline
CIRQ	The CASRO Institute for Research Quality
ClinRO	Clinician Reported Outcome
CRO	Clinical Research Organization
DCF	Data Collection Form
EC	Ethics Committee
EDC	Electronic Data Collection
EU	European Union
eDCF	Electronic Data Collection Form
FAS	Full Analysis Set
FDA	The U.S Food and Drug Administration
GEP	Good Epidemiology Practices
HCP	Healthcare Provider
HRQoL	Health Related Quality of Life
ICF	Informed Consent Form
ICH	International Conference on Harmonisation
IGA	Investigator's Global Assessment
IRB	Institutional/Independent Review Board
Med	Medication
N	Number (typically refers to participants)
PI	Principal Investigator
PRO	Patient Reported Outcome
PROMS	Patient Reported Outcome Measures
PtGA	Patient Global Assessment
QoL	Quality of Life
Qr	Questionnaire

[figure not shown]
---

RCT	Randomized Controlled Trial
RWE	Real World Evidence
SAE	Serious Adverse Event
SAP	Statistical analysis plan
SD	Standard Deviation
SEM	Standard Error of Mean
SOP	Standard Operating Procedure
TBD	To Be Decided
US	United States

## PROTOCOL SUMMARY

Title:	Patient-reported Outcomes for Sarecycline Effectiveness and Safety (PROSES).
Précis:	A prospective cohort study of patients with acne vulgaris (AV) treated with sarecycline and followed for 12 weeks post treatment-initiation. Patient Reported Outcomes (PROs) and clinical profile of patients will be gathered for descriptive analyses of patient outcomes over the 12 week study observation period.
Objectives:	Evaluate PROs and clinician reported outcomes among patients with moderate to severe non-nodular AV who are prescribed sarecycline in clinical practice settings in the U.S.  Primary : Evaluate PROs related to Acne symptoms and impact.  Secondary : Evaluate sarecycline treatment effectiveness, in terms of IGA of AV severity on the face.  Additional : Evaluate clinician satisfaction with sarecycline treatment, sarecycline safety/tolerability, and concordance in perception of facial AV severity among clinicians and patients.
Population:	Three hundred (300) patients of age $\geq 9$ years at the time of initiation of treatment with sarecycline from clinical practices across the U.S. For pediatric patients, their parents/primary caregivers will also be recruited.
Number of Sites:	Maximum of fifty sites will be recruited.
Duration of Treatment	12 weeks.
Study Drug & Mode of Administration	Seysara® tablets; 60 mg, 100 mg, 150 mg, providing a dose of approx. 1.5mg/kg/day; oral. Commercial supply of medication may be supplied to clinical sites/Subjects for the duration of the study.
Study Duration:	Approximately eighteen months of study duration, including study set-up, 12 weeks of subject observation period and study close out followed by study data analyses.

## Schematic of Study Design

*\*Subject screening could be done via phone, prior to Subject's visit to the clinic; or it could be combined with Encounter # 1 (baseline data collection).*

*Clinicians shall prescribe sarecycline (Seysara®) to eligible Subjects per own clinical judgement and manage them as they normally would, in clinical practice.*

## 1 PROSES STUDY RATIONALE

General understanding of acne impact on different aspects of patient HRQoL is still evolving. A real-world study leveraging validated HRQoL instruments such as ASIS questionnaire and the complimentary novel Expert Panel Questionnaire (EPQ; developed using modified delphi method) could help portray a broader picture of impact of acne on pediatric and adult patient HRQoL. Further, assessing the impact of sarecycline treatment on acne patient outcomes, including patient HRQoL, in real-world community practice settings could highlight the humanistic and clinical benefits associated this narrow-spectrum antibiotic treatment option.

## 2 PROSES STUDY OBJECTIVES

### 2.1 Study Objectives

The primary objective of the study is to evaluate PROs in terms of health related quality of life (HRQoL) among patients with moderate to severe non-nodular AV who are administered sarecycline in real-world community practice settings in the U.S. The secondary objective is to evaluate effectiveness of sarecycline treatment, measured by Investigator Global Assessment (IGA) of AV severity on the face.

The additional study objectives include the following evaluations among study Subjects and Site Investigators\*:

- Investigator satisfaction with their sarecycline treatment outcomes.
- Safety and tolerability of sarecycline.
- Comparison of Investigator and Subject perceptions of AV severity.

Note: Dermatologists are expected to predominantly constitute the Site Investigator category, while a few physician assistants and nurse practitioners may be included in the study, reflecting the routine care management of acne in community practice settings.

## 2.2 Study End Points

The primary endpoint of the study will be the PROs, in terms of self-perceived acne symptoms and impact of acne on emotional functioning, social functioning and activities of daily living, at Week 12.

The secondary endpoint will be the proportion of Subjects with Facial IGA success at Week 12, defined as a 2-point decrease in IGA score from baseline and a score of 0 (clear) or 1 (almost clear).

Additional endpoints of the study will include:

- Proportion of Subjects for whom Site Investigator reported 'very satisfied' or 'satisfied' in the question on global satisfaction with sarecycline treatment, at Week 12.
- Description of changes in PROs from baseline, at Week 12.
- Frequency of documented adverse events (AEs) and severe adverse events (SAEs) during the 12-week study observation period.
- Comparison of Subject perception and Site Investigator perception of AV severity, at Week 12.

## 3 STUDY DESIGN

This is a single-arm, prospective cohort study which will enroll patients with moderate to severe acne vulgaris (AV) who are prescribed sarecycline in real-world community practices in the U.S. Caregivers also enrolled in the study, in case of pediatric patients. Study Subjects were followed for up to 12 weeks post-index date (with the 'index-date' defined as the date of initiation of sarecycline). Study Site Investigators and Subjects completed online surveys at baseline (at time of study enrollment) and at weeks 4, 8 and 12, post-index date.

This study entailed provision of sarecycline treatment to study participants. Site Investigators decided on who to prescribe sarecycline as part of usual care, based on their best clinical judgment, prior to subject recruitment. The study is sponsored by Almirall, hereinafter referred to as the

Sponsor. The study is managed by Avant Health, hereinafter referred to as the Contract Research Organization (CRO).

### **3.1 Subject Inclusion Criteria**

**Patient Inclusion Criteria:** In order to be eligible to participate in this study, an individual must meet all of the following criteria:

- Male or female, aged 9 years and above at the time of study recruitment.
- Has facial non-nodular AV with IGA score of moderate (3) or severe (4).
- Considered as a potential candidate for sarecycline treatment to manage their AV, per clinician's judgment.
- Able to read and write English.
- Provide consent (in case of adult patients) or assent (in case of pediatric patients) to participate in the study.
- Willing to comply with all study procedures and be available for the duration of the study.

**Caregiver Inclusion Criteria:** In order to be eligible to participate in this study, an individual must meet all of the following criteria:

- Male or female, aged 18 years and above.
- Able to read and write English.
- Primary caregiver of the study-eligible patient.
- Provide consent to participate in the study.
- Willing to comply with all study procedures and be available for the duration of the study.

### **3.2 Subject Exclusion Criteria**

An individual who meets any of the following criteria were excluded from participation in this study:

- Patients with any dermatological or physical condition of the face that could interfere with the AV clinical evaluations.
- Patients with any history of allergy to tetracycline-class antibiotics, pseudomembranous colitis or antibiotic-associated colitis.
- Patients with any known resistance to other tetracyclines.
- Patients currently treated with any of the following: penicillin, oral retinoids (incl. Isotretinoin and acitretin).
- Among female Subjects: Currently pregnant, lactating, or is planning a pregnancy during the study period.
- Patients or their caregivers are unable to comply with the requirements of the study or patients who in the opinion of the Site Investigator should not participate in the study.
- Patients for whom medical chart is inaccessible to Site Investigators to complete baseline data collection.

#### 4 STUDY SCHEDULE & PROCEDURES

Study eligible patients who were considered as candidates for sarecycline treatment as part of usual care Acne management were screened, consented and recruited into the study, followed for up to 12 weeks post-index date, encompassing four distinct data collection encounters, namely, baseline, week-4, week-8 and week-12, post-index date. Index date is the date of initiation of sarecycline treatment (at baseline), when the subject was prescribed sarecycline.

Different data elements were collected from Site Investigators and from study Subjects at these data collection encounters, as outlined below. For patients of age 12yrs and older, acne patients themselves completed relevant PRO elements pertinent to study endpoints, at all encounters; for patients of age 9-11yrs, parents/caregivers of pediatric patients completed the PRO elements at all encounters, serving as a proxy, upon consulting with their child on question responses.

The schedule of events is summarized in Appendix A.

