### **6.3.2 *Subgroup Analysis***

Primary and select additional outcome measures (as individually identified in the following sections) will be summarized and repeated for the following subgroups, using FAS:

- Gender: male and female
- Age groups: 9 to 17 years and  $\geq 18$  years
- Race: white, african-american/black, other

- Body mass index: < 25 kg/m^2 and ≥ 25 kg/m^2
- Baseline facial IGA score: moderate and severe
- Concomitant use of contraceptives in females: yes and no

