#### 6.4 Primary Endpoint Analysis

The primary endpoint of PROs at Week 12 will be assessed descriptively, using the FAS dataset.

For ASIS questionnaire, the individual item and domain/subscale scores will be created per instrument developer instructions, analyzed descriptively for the baseline and Week 12 encounters, treating the responses as categorical variables and/or continuous variable, as appropriate. For the overall questionnaire data evaluation, no missing data imputation will be applied to compute domain/subscale scores.

The Patient Global Assessment (PtGA) of acne severity based on the single ASIS item (# 9) will be analyzed separately using descriptive statistics and reported for Week 12. Specifically, proportion of Subjects who reported clear (0) and almost clear (1) on the item scale at Week 12 will be assessed. Last Observation Carried Forward (LOCF) data imputation method will be used to impute responses to ASIS item # 9 at Week 12 for the Subjects with missing data at Week 12.

Patient self-rating of their appearance based on the single ASIS Item (# 10) will be analyzed separately using descriptive statistics and reported for Week 12. Specifically, proportion of Subjects reporting "very good" or "excellent" at Week 12 will be assessed. LOCF data imputation method will be used to impute responses to ASIS item # 10 at Week 12 for the Subjects with missing data at Week 12.

For EPQ, the items will be analyzed individually using descriptive statistics and reported for Week 12.

For all PRO elements, descriptive statistics will be computed. ASIS summary domain scores, ASIS item # 9, ASIS item # 10, and individual EPQ items will be stratified by age and other subgroups outlined in Section 6.3.2, to explore the relationship between these HRQoL items and subject characteristics.

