#### **6.6.5 Comparison of Parent/Caregiver and Patient Perceptions of AV Severity and Impact**

Parent/caregiver and pediatric patient responses to the questions related to AV severity at Baseline and Week 12 will be compared and reported using descriptive statistics, to portray the

level of concordance/discordance in stakeholder perceptions, within the Subject age group of 12-17 yrs. This analysis will be conducted using FAS.

Responses to select EPQ items at Baseline and Week 12 related to worries about Acne and impact of acne on child's ability to reach future goals will be compared to corresponding questions to parents/caregivers to portray the level of concordance/discordance in stakeholder perceptions, within the Subject age group of 12-17 yrs. This analysis will be conducted using FAS.

Parent/caregiver and pediatric patient responses to the questions at Week 12 related to the parents' understanding of child's concerns will be compared and reported using descriptive statistics, to portray the level of concordance/discordance in stakeholder perceptions, within the Subject age group of 12-17 yrs. This analysis will be conducted for the entire relevant cohort using FAS.

No missing data imputation will be undertaken for these items.

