**Table 7.1.11. Sub-group Analysis of ASIS Domain Scores**

	Baseline				Week 12			
	Symptom	Impact	Emotional Impact	Social Impact	Symptom	Impact	Emotional Impact	Social Impact
Sex:								
Male	n, Mean	n, Mean	n, Mean	n, Mean	n, Mean	n, Mean	n, Mean	n, Mean
Female	n, Mean	n, Mean	n, Mean	n, Mean	n, Mean	n, Mean	n, Mean	n, Mean
p-value	p	p	p	p	p	p	p	p
Age Group:								
≥ 9 and < 12 years								
≥ 12 and < 18 years								
≥ 18 years								
p-value								
Race:								
White								
African								
American/Black								
Other								
p-value								
Body mass index:								
< 25 kg/m 								
≥ 25 kg/m 								
p-value								
Baseline facial IGA:								
Moderate								
Severe								
p-value								
Female who used oral contraceptive*:								
Used								

Did not use

*p*-value

\* The denominator for the percentage is the number of 'female' subjects with available data (N=X for baseline and N=X for week 12).

Note: P-values refer to the statistical difference between the means of subgroups for a given variable, at a given timepoint.

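### In the exploratory PRO age-subgroup tables the 9-11 row is all caregiver proxy report and the older rows are all self-report, so the age p-value cannot separate age from respondent

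*SAP*

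**What the plan says.** SAP section 4 sets the respondent by age. From 12 upward: "For patients of age 12yrs and older, acne patients themselves completed relevant PRO elements pertinent to study endpoints, at all encounters". For ages 9-11: "parents/caregivers of pediatric patients completed the PRO elements at all encounters, serving as a proxy". The same sentence adds that this was done "upon consulting with their child on question responses". Protocol section 7 has the same rule.

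SAP 2.2 defines the primary endpoint at Week 12 "in terms of self-perceived acne symptoms and impact of acne on emotional functioning", with social and daily-living impact also covered. SAP 6.4 says of the ASIS domain scores, ASIS items 9 and 10 and each EPQ question that they "will be stratified by age and other subgroups outlined in Section 6.3.2, to explore the relationship between these HRQoL items and" the patients' characteristics.

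The text and the table shells define age differently. SAP 6.3.2 lists two groups ("Age groups: 9 to 17 years and" 18 or older). The PRO shells (Tables 7.1.7.1-7.1.7.11, 7.1.11, 7.1.16.1 and 7.1.16.2) print three rows, the first being "≥ 9 and < 12 years", and one p-value per visit. In the EPQ shells and Table 7.1.16.2 the third row reads ≥ 12 years, which overlaps the 12-17 row; in Tables 7.1.11 and 7.1.16.1 it reads ≥ 18 years.

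SAP 6.3.1 (Overview) names chi-square tests for discrete measures and independent-sample t-tests for subgroup means. It calls all such tests exploratory and treats P ≤ 0.05 as significant.

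**The concern.** No patient aged 9-11 self-reports, and no older patient's ASIS or EPQ answer in these tables is a proxy answer. A comparison that sets the 9-11 row against the others therefore changes age and respondent together. Its null hypothesis is that there is neither an age effect nor a proxy-versus-self reporting difference. A small p-value can come from either, and no model fitted to these rows can tell them apart.

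The stated purpose of the strata is to relate the PROs to subject characteristics, and who filled in the form is not one. A reader of a table with no respondent footnote would take a significant result as an age pattern in self-perceived acne burden.

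**Working it through.** **Which tests are affected.** EPQ10 (parents' understanding) is left out because SAP 5.4 says patients aged 12-17 were asked it, so the 9-11 row of Table 7.1.7.10 should be empty rather than proxy-filled. The remaining age p-values are:

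- EPQ: 10 items × 2 visits = 20
- ASIS domain and subscale scores: 4 × 2 visits = 8
- ASIS items 9 and 10: 2 × 4 visits = 8
- Total: 20 + 8 + 8 = 36

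The clinician-rated age tables (7.2.4.5, 7.2.4.8, 7.2.9) are not affected.

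**Inputs.** The plan has no power or error-rate figure to reproduce; SAP 6.1 says no formal calculation was made. From the documents: about 300 enrolled, a full analysis set of Week 12 completers (so at most 300), and a threshold of 0.05. Assumed: N = 250 (300 also tried), n = 5 to 30 patients aged 9-11, no true age effect, and a reporting gap of d standard deviations in the 9-11 row only. A three-group F test is also assumed, because the SAP names only a two-group t-test and the shells have three rows, read here as 9-11, 12-17 and 18 or older.

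**Three rows, continuous score.** The F statistic has 2 and N − 3 degrees of freedom and noncentrality λ = d² × n × (N − n)/N. The split of the remaining patients between 12-17 and adults does not enter λ. Example: N = 250, n = 10, d = 0.5 gives λ = 0.25 × 10 × 240/250 = 2.40 and rejection probability 26%.

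| Patients aged 9-11 (N = 250) | d = 0 | d = 0.25 | d = 0.5 |
|---|---|---|---|
| 5 | 5% | 7% | 15% |
| 10 | 5% | 10% | 26% |
| 15 | 5% | 12% | 37% |
| 20 | 5% | 15% | 46% |
| 30 | 5% | 19% | 62% |

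Simulation of the F test at N = 300 and d = 0.5 gave 25.9% with 10 proxies and 46.9% with 20, against 26.3% and 47.1% by formula.

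**Three rows, proportion.** For a 3 × 2 chi-square with N = 250, a true rate of 50% and 40% of the other patients aged 12-17, a 15-point gap gives 6.8%, 11.2%, 14.7%, 18.6% and 25.4% with 5, 10, 15, 20 and 30 proxies. A 25-point gap gives 10.9%, 25.4%, 37.0%, 48.3% and 65.1%.

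**Two groups as in SAP 6.3.2.** Pooling 9-17 shrinks the shift to d × n/(n + t), where t is the number aged 12-17. With N = 300, n = 20, t = 112 and d = 0.5 the shift is 0.5 × 20/132 = 0.076 SD. Rejection at d = 0.5 is then 5.3%, 6.3%, 10.0% and 15.5% with 5, 10, 20 and 30 proxies.

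**Self-reporters only (12-17 versus 18 or older).** The proxy gap drops out. Rejection is 5.0% for scores and 4.7-5.1% for proportions, whatever the gap.

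**The case against.** The strongest reply has four parts.

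- **The tests are exploratory.** No age hypothesis exists and the primary endpoint is assessed descriptively. This stands, and it limits the harm to interpretation. It does not change what the printed p-value measures.
- **The caregiver consults the child first.** This may make the gap small. It does not break the aliasing, because the whole row is still completed by caregivers.
- **The sizes are conditional.** Nothing in the documents supports a particular gap or number of children. With 5 proxies and a 0.25-SD gap the rate is only about 7%. This stands in full; the figures show what could happen, not what to expect.
- **The SAP is partly open about the source.** The note to Table 7.3.1 says ages 9-11 are caregiver data, and Table 7.3.3 isolates them for acne severity. That is true, but the PRO age tables carry no such note.

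A reader might go further and infer that the overall Week 12 PRO result is compromised because a self-perceived endpoint contains proxy answers. The documents do not support that. Under the assumptions above, a 0.5-SD gap in 10 to 30 of 250 patients moves a pooled mean by 0.5 × 10/250 = 0.02 to 0.5 × 30/250 = 0.06 SD. The same respondent rule applies at every encounter, so a constant gap cancels in change from baseline.

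A reader might also infer that the SAP expects parents and patients to disagree. SAP 6.6.5 only sets out to portray the "level of concordance/discordance in stakeholder perceptions, within the Subject age group of 12-17 yrs"; it predicts neither direction nor size.

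**Conclusion.** The point holds for the 13 PRO age-subgroup tables other than the EPQ10 table: their age p-value cannot be read as an age effect while the 9-11 row is in the test. That follows from the respondent rule and the table layout alone. The size does not: the ranges of about 7-19% (0.25 SD) and 15-62% (0.5 SD) rest on N = 250, 5 to 30 proxies, no age effect and an F test that the SAP does not name. Under the two groups of SAP 6.3.2 the range is about 5-16% at 0.5 SD with N = 300. It would be equally unsupported to say that any age difference seen is only a reporting artefact; the data could not show that either. This is a worthwhile correction to exploratory subgroup rows and does not threaten the main Week 12 findings.

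**What to change.** 1. Reconcile the age groups of SAP 6.3.2 with the shells, and correct the third row that reads ≥ 12 years in the EPQ shells and Table 7.1.16.2.
2. In Tables 7.1.7.1-7.1.7.9, 7.1.7.11, 7.1.11, 7.1.16.1 and 7.1.16.2, compute the age p-value on self-reporters only, 12-17 versus 18 or older. This is a two-group comparison, so the t-test and chi-square already named in SAP 6.3.1 suffice.
3. Keep 9-11 as a descriptive row footnoted as caregiver proxy, without a p-value. The wording of the Table 7.3.1 note can be adapted.
4. If the 12-17 parent-child comparisons (Tables 7.3.4, 7.3.6 and 7.3.7) are cited on the likely respondent gap, call them a rough guide only. Those caregivers gave their own view, not a consulted proxy answer, and their children are older.

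Self-report-only repeats of the overall change tables (7.1.6.2, 7.1.9, 7.1.10) are optional and should add little.

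The cost is SAP wording and re-running a limited set of tables, with no new data. The one loss is the p-value involving the 9-11 row.
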